**Noninvasive Ventilation for Preterm Neonates With
Respiratory Distress Syndrome: a Multi-center Randomized
Controlled Trial**

(NCT03099694)

13 July 2017

Solid PDF/A Express
<http://www.SolidDocuments.com/>

STUDY PROTOCOL

Noninvasive high-frequency oscillatory ventilation versus nasal continuous positive airway pressure in preterm infants with respiratory distress syndrome: Study protocol for a multi-center, prospective, randomized, controlled trial. For the Noninvasive High-Frequency Oscillatory Ventilation Study Group (NHFOV Study Group*).

Abstract

Background: Invasive mechanical ventilation is associated with development of adverse pulmonary and non-pulmonary outcomes in very low birth weight infants. Various modes of non-invasive respiratory support are being increasingly used to decrease the incidence of bronchopulmonary dysplasia (BPD). The aim of this trial is to compare the effect of noninvasive high-frequency oscillatory ventilation (NHFOV) and nasal continuous positive airway pressure (NCPAP) in preterm infants with respiratory distress syndrome (RDS) as a primary noninvasive ventilation support mode.

Methods/Design: In this multicenter, randomized, controlled trial, 300 preterm infants born at gestational age (GA) less than 34 weeks with a diagnosis of RDS will be randomized to NHFOV or NCPAP as a primary mode of noninvasive respiratory support. Study will be conducted in 18 tertiary neonatal intensive care units in China. The primary outcome is the need for invasive mechanical ventilation (IMV) during the first 7 days after enrollment in preterm infants randomized to the two groups. The

prespecified secondary outcomes include days of hospitalization, days on noninvasive respiratory support, days on IMV, days on supplemental oxygen, mortality, need for surfactant, severe retinopathy of prematurity(ROP) requiring laser or surgery, patent ductus arteriosus needing ligation, bronchopulmonary dysplasia(BPD), occurrence of abdominal distention, air leaksyndromes, intraventricular hemorrhage (IVH \geq grade 3), necrotizing enterocolitis (NEC \geq II stage) and nasal trauma. Other secondary outcomes include Bayley Scales of Infant Development at 18-24 months of corrected age.

Trial registration: ClinicalTrials.gov Identifier: NCT03099694.

Key words: Noninvasive high-frequency oscillatory ventilation; nasal continuous positive airway pressure; respiratory distress syndrome; preterm infants; surfactant; invasive mechanical ventilation

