Background

Respiratory distress syndrome (RDS) due to surfactant deficiency is the leading cause of respiratory failure in preterm infants [1]. Early noninvasive positive pressure ventilation has become a recommended strategy for respiratory management of preterm infants with RDS [2]. In addition to nasal continuous positive airway pressure (NCPAP), various types of noninvasive ventilation (NIV) modes have been used in the treatment of RDS including heated, humidified, high-flow nasal cannula (HHFNC), biphasic NCPAP (BP-NCPAP) and nasal intermittent positive airway pressure (NIPPV) [3]. However, clinical trials have shown that 25 to 67% of very low birth weight preterm infants fail these NIV modes and require IMV [4-5]. To minimize the need of IMV, noninvasive high-frequency oscillatory ventilation (NHFOV) has been studied as a rescue treatment after failure of other NIV modes or following extubation from IMV during weaning phase [6]. However, to date, no studies have been published on the efficacy of NHFOV as a primary mode of respiratory support in preterm infants. In the present trial, we aim to compare the effect of NHFOV and NCPAP in preterm infants with RDS as a primary NIV mode. Our main hypothesis is that NHFOV is more effective in the treatment of preterm infants with RDS than NCPAP when used as a primary NIV mode.

Trial Design

Aim

The primary aim of this trial is to compare the need for IMV during the first 7 days of life in infants randomized to NHFOV versus NCPAP.

Study design

This will be a multi-center, prospective, randomized controlled trial conducted in 18 tertiary neonatal intensive care units (NICUs) in China. The trial will be performed in accordance with prospective trial flow (Fig.1).

Inclusion criteria:

(1) Gestational age (GA) is from 26 weeks 0 days (26⁺⁰weeks) to 33 weeks 6 days(33⁺⁰weeks) (estimated on the postmenstrual date and early gestation ultrasonographic findings); (2) diagnosis of RDS. The diagnosis of RDS will be based on clinical manifestations(tachypnea, nasal flaring and or grunting) and the typical X-ray picture of RDS (grain shadow, air bronchogram or white lung)-see appendix; (3) RDS Silverman score>5; (4) Age <12 hours; (5) informed parental consent has been obtained.

Exclusion criteria

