(1) Resuscitation requiring early intubation according to the American Academy of Pediatrics guidelines for neonatal resuscitation [8]; (2)major congenital malformations or known complex congenital heart disease; (3)pulmonary hemorrhage or pneumothorax; (4) congenital lung diseases or malformations or pulmonary hypoplasia;

Setting

We plan to enroll preterm infants born between 26 and 34 weeks of gestational age from 18 tertiary NICUs in China. These 18 tertiary NICUs have more than 800 NICU beds and annual admissions of nearly 8,000 preterm infants with RDS each year. The first (XZ) and last authors (RR) take responsibility for the accuracy and completeness

of the trial.

Randomization

To avoid the chance of having more infants in one group than another, block randomization will be applied, with a block size of 4. The envelopes are sealed, shuffled, and then numbered in sequential order from 1 to 4. A clinician who is not in the trial group will open the envelope and randomize patients. This procedure will be repeated for each group of four infants. Infants will be stratified according to 26^{0/7}-27^{6/7} weeks, 28^{0/7}-29^{6/7} weeks, 30^{0/7}-31^{6/7} weeks and 32^{0/7}-33^{6/7} weeks. Infants born from multiple gestations will be assigned by individual randomization. Infants randomized to one arm cannot crossover to the other or vice-versa during the study.

Trial intervention

Ventilators

CPAP: CPAP will be provided by continuous flow devices (CNO Medin, Germany or Carefusion, USA) Bubble CPAP devices will not be used.

NHFOV: NHFOV will be provided by two ventilators (CNO, Medin, Germany or SLE 5000, UK). The Medin CNC ventilator produces high-frequency oscillations by flow interruption with cyclic opening-closure of the end expiratory valve. Otherwise, The SLE 5000 ventilator is a time-cycled, pressure-limited and continuous-flow neonatal ventilator.

Before the beginning of the study all ventilators will be checked to ensure that there is no malfunction.

Interfaces

CPAP and NHFOV will be all administered through short, low-resistance binasal prongs,

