The primary outcome of this trial will be to determine the need for IMV in the first 7 days of life in preterm infants randomized to the two groups. Secondary outcomes include days of hospitalization, days on noninvasive ventilation, days on supplemental oxygen, pre-discharge mortality, surfactant doses, incidence of stage III ROP and BPD, occurrences of abdominal distention, air leaks, IVH \geq grade 3 and NEC. Secondary outcomes also include Bayley Scales of Infant Development at 18-24 months of corrected age. BPD will be defined according to the National Institutes of Health consensus definition as mild, moderate and severe BPD [12], IVH classification according to Papile et al [13] and for NEC, Bell staging will be used [14].

Data collection

Patient demographic data include: sex, birth weight, gestational age, Apgar scores, mode of

delivery, prenatal corticosteroid use, premature rupture of the membrane, RDS Silverman score and critical risk index for babies-II (CRIB-II) score. More details see in the appendix Clinical data :Including the need for IMV, days of hospitalization, days on noninvasive respiratory support, days on supplemental oxygen, mortality, the need for surfactant, occurrences of abdominal distention, air leaks, IVH \geq grade and NEC \geq stage II. More details see in the appendix Follow-up data: The incidence of BPD and ROP at a post-menstrual age of 36 weeks or at discharge, and Bayley Scales of Infant Development at 18-24 months of corrected age.

Sample size calculation

It is difficult to calculate a sample size for such a study, since it is the first to investigate NHFOV vs CPAP in primary support phase in preterm infants with RDS. There is only one preliminary study available about the primary outcome “need for IMV”. This pilot study conducted by Zhu et al provides data about the primary outcome “need for IMV”. This trial showed the need for IMV was significantly lower in the NHFOV compared with the NCPAP group (24.3% vs. 56.4%, $P < 0.01$). Considering an α -error of 0.05 and a power of 90%, 150 neonates should be enrolled in each arm (with a 1:1 design) to detect the same difference.

Statistical methods

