Data will be analyzed using SPSS version 19 software. The statistical analyses include Student's t-test for continuous data and compared proportions using Chi-squared test, and Fisher's exact test for categorical data. Predefined four subgroups are 26^{0/7}-27^{6/7} weeks, 28^{0/7}-29^{6/7} weeks, 30^{0/7}-31^{6/7} weeks and 32^{0/7}-33^{6/7} weeks, and subgroup analyses will be conducted for the primary outcome in the preterm infants. To further evaluate the effect of NHFOV on intubation within

subgroup, the test of treatment-by-gestational age subgroup interaction will also be done using the paired binary logistic regression. For the preterm infants lost to follow-up, the missing values of the primary and secondary outcomes are replaced using multiple imputation. A P -value < 0.05 will be regarded as statistically significant.

Data Safety Monitoring Board (DSMB): [name], Professor of Pediatrics, Oklahoma University Medical Center, Oklahoma, [name], Professor of Pediatrics, Medical College of Georgia, Georgia Health Sciences University, Augusta, Georgia, and [name], MD., MPH (Biostatistics and Epidemiology) Assistant Professor of Pediatrics, Keck School of Medicine of the University of Southern California, Los Angeles, California will serve as DSMB members. [name] will also serve as consultant for statistical analysis.

Registration number

The trial has been approved by the centralized ethics committee (The Ethics Committee of Daping Hospital, Research Institute of Surgery, Third Military Medical University) and registered at <http://www.clinicaltrials.gov>(ID: NCT03099694).

Discussion

In the past decades, several clinical trials have compared the effects between NHFOV and NCPAP in neonates as a rescue mode or during weaning from IMV. These trials demonstrated that NHFOV applied with nasopharyngeal tube are more beneficial than NCPAP in reducing CO₂ levels [16-19]. Recently, two retrospective case series also reported NHFOV could be applied in preterm infants as a rescue treatment after the

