Male infants																Female infants																
Birthweight (g)	2751 to 3000																															0
	2501 to 2750																															1
	2251 to 2500																															3
	2001 to 2250																															2
	1751 to 2000																															3
	1501 to 1750																															6
	1251 to 1500																															5
	1001 to 1250																															3
	751 to 1000	12	10	9	8	8	7	6	5	4	3	3	2	1	0	0	11	10	8	7	6	5	4	3	3	3	3	2	1	1		
	501 to 750	14	13	12	11	10	9	8	8	8	8	8	6	6	6	13	12	11	10	9	8	7	6	5	5	5	5	5	5			
251 to 500	15	14	13	12	11	10	10								14	13	12	11	10	10												
Gestation (weeks)																Gestation (weeks)																

Temperature at admission (°C)

≤29.6	5
29.7 to 31.2	4
31.3 to 32.8	3
32.9 to 34.4	2
34.5 to 36	1
36.1 to 37.5	0
37.6 to 39.1	1
39.2 to 40.7	2
≥40.8	3

Base excess (mmol/L):

<-26	7
-26 to -23	6
-22 to -18	5
-17 to -13	4
-12 to -8	3
-7 to -3	2
-2 to 2	1
≥3	0

Sex, birthweight (g) and gestation (weeks):	_____
Temperature at admission (°C):	_____
Base excess (mmol/L):	_____
Total CRIB II Score	_____

The logistic regression equation relating CRIB II to mortality (CRIB II algorithm) is:
 Log odds of mortality = $G + 6.47 + 0.450 \times \text{CRIB II}$
 Probability of mortality = $\exp(G) / (1 + \exp(G))$
 The range of possible CRIB II scores is 0 to 27

Clinical risk index for babies II (CRIB II) score

- **Premature rupture of the membrane.** Premature rupture of the membrane will be considered complete if more than 18 hours.
- **Abdominal distension.** Abdominal circumference (cm) at 48h and 96h after study intervention.

References

3. Cumming JJ, Polin RA, AAP the COMMITTEE ON FETUS AND NEWBORN. Noninvasive respiratory support. Pediatrics2016; 137(1):

e20153758. <http://dx.doi.org/doi: 10.1542/peds.2015-3758>.

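### Abdominal distension is listed as an occurrence but defined only as circumference at 48 h and 96 h, with no event criterion, deciding time point or specified pre-support measurement

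*Combined protocol and SAP*

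**What the plan says.** The Abstract lists "occurrence of abdominal distention" as a secondary outcome. The Outcomes section uses the plural form, "occurrences of abdominal distention", and Data collection repeats it among the clinical data. The only definition is in Appendix A3: "Abdominal circumference (cm) at 48h and 96h after study intervention".

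The baseline list under Data collection ("Patient demographic data include: sex, birth weight, gestational age, Apgar scores, mode of" delivery, and so on) includes birth weight and gestational age but not abdominal circumference. That section refers to the appendix for more detail, and the appendix as provided adds no baseline circumference.

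Statistical methods offers "Student's t-test for continuous data and compared proportions using Chi-squared test", with Fisher's exact test also for categorical data. It does not say which applies to this outcome, and it names no covariate adjustment for it.

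**The concern.** The outcome's name calls for a yes/no event, and its definition supplies two lengths. Two analysts following the plan could report different things: a proportion with a cut-off of their own choosing, a mean at 48 h, a mean at 96 h, or some combination.

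The baseline gap matters more than the wording. An analyst can choose a model later, but cannot recover a pre-support circumference that was never taken. Without it, no event defined by an increase from baseline can be constructed. An absolute cut-off would partly sort infants by body size, because eligibility spans almost eight weeks of gestation.

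At stake is one named secondary comparison of the two modes of support. The primary outcome is not affected.

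**Working it through.** **1. Can an occurrence be derived?** Set the places side by side.

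| Needed for an event | What the documents give |
|---|---|
| Measured quantity | Circumference in cm (Appendix A3) |
| Threshold, sign or grade | None |
| Reference value before support | None specified (Data collection; Appendix A1 to A3) |
| Time point, or rule for combining two | 48 h and 96 h, no rule (Appendix A3) |
| Test | t-test or chi-squared/Fisher, depending on an outcome type that is not settled (Statistical methods) |

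The answer is no. A change from a pre-support value cannot be derived either. A change from 48 h to 96 h can be, but both values come after support has started (the times are read here as hours from its start).

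**2. What does the raw comparison lose?** The plan gives no SD, event rate, effect size or power for this outcome, so there is no figure to reproduce.

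Inputs from the documents: 150 per arm, 1:1, and alpha 0.05 (Sample size calculation). Assumptions: two-sided test, complete data, SD of circumference 1.5 to 3.5 cm, and correlation r of 0.5 to 0.9 between baseline and follow-up.

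Detectable difference without adjustment, 80% power:

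(z₀.₉₇₅ + z₀.₈₀) × SD × √(2/150) = (1.960 + 0.842) × 0.1155 × SD = **0.32 SD**

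At 90% power: (1.960 + 1.282) × 0.1155 × SD = 0.37 SD.

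Adjusting for baseline multiplies the SD by √(1 − r²). At 80% power:

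- r = 0.5: 0.3235 × 0.866 = 0.28 SD
- r = 0.8: 0.3235 × 0.600 = 0.19 SD
- r = 0.9: 0.3235 × 0.436 = 0.14 SD

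In centimetres, at 80% power:

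| Assumed SD (cm) | Unadjusted | r = 0.5 | r = 0.8 | r = 0.9 |
|---|---|---|---|---|
| 1.5 | 0.49 | 0.42 | 0.29 | 0.21 |
| 2.5 | 0.81 | 0.70 | 0.49 | 0.35 |
| 3.5 | 1.13 | 0.98 | 0.68 | 0.49 |

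Power for a given true difference (two-sample normal approximation, same inputs):

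| True difference | SD (cm) | Unadjusted | Baseline-adjusted, r = 0.8 |
|---|---|---|---|
| 0.5 cm | 1.5 | 82% | >99% |
| 0.5 cm | 2.5 | 41% | 82% |
| 0.5 cm | 3.5 | 24% | 54% |
| 1.0 cm | 1.5 | >99% | >99% |
| 1.0 cm | 2.5 | 93% | >99% |
| 1.0 cm | 3.5 | 70% | 98% |

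Small differences can be missed without adjustment. Larger ones are still found.

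**The case against.** The strongest reply is that a randomised comparison of post-treatment circumference needs no baseline to be valid. Under Randomization, "Infants will be stratified according to" four two-week gestational-age bands, so body size is not expected to differ between arms. Variation in size costs precision and does not cause bias. This stands. A reader might infer that body size swamps any effect, or that a real difference could be neither detected nor described. The documents give no SD or expected effect to support that, and the table above runs against it.

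Birth weight and gestational age are already collected, and adjusting for them would recover some precision with no new measurement. This also stands, and it means that the gain from a baseline circumference should not be judged only against no adjustment. For illustration, with assumed values: if birth weight and gestational age explain the outcome with R = 0.6 and adding baseline raises R to 0.8, the residual variance ratio is 0.64/0.36 = 1.8. Starting from R = 0.7 it is 0.51/0.36 = 1.4. But Statistical methods plans no such adjustment, and it would supply neither an event definition nor a change from baseline.

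Two further limits apply. The documents never call abdominal distension a safety outcome; it is one of many secondary outcomes. And the absence of a baseline value is read from what was provided. The appendix contains no case report form, so one cannot say that no site will take the measurement, only that none is specified.

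**Conclusion.** The point holds in a limited form. As written, neither an occurrence of abdominal distension nor a change from baseline can be derived; this rests on the text alone and needs no assumption. The unadjusted comparison of raw circumference is valid but less precise than it could be. The detectable difference at 80% power is about 0.32 SD, against about 0.28 to 0.14 SD with a baseline measurement. Those figures rest on 150 infants per arm with complete data, a two-sided 0.05 test and an assumed correlation of 0.5 to 0.9. Part of the gain is available from covariates already collected. The matter is minor, since it concerns one secondary outcome, but a missing baseline cannot be repaired after enrolment.

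**What to change.** - Record abdominal circumference once, just before study support starts.
- Analyse the 48 h and 96 h values by ANCOVA, adjusted for baseline circumference and gestational-age stratum. Where baseline is missing, adjust for birth weight and gestational age instead.
- Name one of the two times as the main one.
- Either rename the outcome as abdominal circumference in the Abstract, Outcomes and Data collection, or have the investigators prespecify, before enrolment, the relative increase from baseline that counts as an occurrence. The choice of threshold is theirs.

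The cost is one tape measurement and one case report form field per infant, plus a few sentences in Appendix A3 and Statistical methods. The sample size does not change.
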